13.7 Secondary Analysis Plans

A key secondary analysis will be to repeat the primary analysis that defines a tumor response by central review using iRECIST criteria.

For the secondary time-to-event endpoints, stratified Cox models will be used to compare the outcomes between the two treatment groups. This includes PFS and OS. The subgroup analyses will be done using a stratified Cox model that includes the treatment arm assignment as an explanatory variable and a separate model will be generated for each level for the subgroup of interest. The results will be summarized with a forest plot displaying the estimate of the hazard ratio and corresponding 95% confidence interval.

The rates of treatment discontinuation at one year will be summarized with a binomial point estimate and corresponding 95% confidence interval by arm. The denominator will be all patients randomized to the treatment arm and who are still alive and progression-free at one year and the numerator will be the number of patients who are alive and progression-free at one year and discontinued the protocol

treatment prior to one year. A comparison between the rates will be performed with a chi-square test or a Fisher's exact test if the assumptions of the chi-square test are violated.

Adverse events will be summarized with frequencies and relative frequencies. The maximum grade for an AE will be recorded for each patient by treatment arm. The number (percent) of patients that experience each observed adverse event will be summarized by treatment arm. In addition, the proportion of patients that experience a grade 3+, grade 4+, and grade 5 adverse event will be summarized as the number and percent of patients by treatment arm. The primary summary will be regardless of attribution. We will also do an analogous summary of the adverse events that were deemed at least possibly related to treatment.

To evaluate between-arm differences in patient-reported adverse events as assessed by the PRO-CTCAE from baseline through 24 months, the frequency and proportion of patients with a maximum post-baseline score greater than 0 will be compared across arms using a χ^2 test or Fisher's exact test with a nominal significance level of $\alpha = .10$. Similarly, the frequency and proportion of patients with a maximum post-baseline score greater than or equal to 3 will be compared across arms using a χ^2 test or Fisher's exact test with a nominal significance level of $\alpha = .10$. The same procedure will be applied to patients' maximum baseline-adjusted scores. Patients' maximum baseline-adjusted scores will be calculated using the method described by Dueck et al. If the patient's maximum post-baseline score is greater than his/her baseline score, then the patient's maximum baseline-adjusted score will equal his/her maximum post-baseline score; otherwise, if the patient's maximum post-baseline score is less than or equal to his/her baseline score, then the patient's maximum baseline-adjusted score will equal 0. The aforementioned analyses will be based on all available PRO-CTCAE data. However, the proportion of, and reported reasons for, missing data will be presented by time point and arm. Correlation analysis and logistic regression analysis will be used to examine whether baseline patient characteristics and prognostic factors predict missingness. As a sensitivity analysis, multiple imputation may be performed to assess the robustness of results across different assumptions about the missing data. Since a preferred or optimal statistical methodology for PRO-CTCAE data is yet to be determined, additional analyses of PRO-CTCAE data beyond those specified above may be undertaken based on the current state of the science at time of data maturity for this study.

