1.2 Registration Patient Reported Outcomes (PROs) and Quality of Life (QOL) Measurements

PROs, particularly involving symptomatic toxicities, provide discrepant yet complementary information compared with clinician interpreted data^{12–16}. In particular, greater sensitivity for adverse event reporting, auxiliary characterization of performance status and earlier detection of symptoms^{12,14,17–20}. Implementation of PRO systems has shown feasibility in the clinical trial setting demonstrating 78% to 96% adherence^{21,22} and several studies report that baseline PRO and QOL data may prognosticate survival better than performance status in clinical trials^{23–25}. A landmark prospective study also now suggests that serial monitoring of patient reported symptoms may improve median overall survival by up to 5 months for patients undergoing treatment of solid malignancies²².

QOL measurements of fatigue and overall perception of QOL are routinely included in Alliance studies and will be assessed upon registration in this study. Baseline single-item assessments of fatigue and overall QOL are strong prognostic indicators for survival in cancer patients, independent of performance status^{26–28}. Routine inclusion of these measures should be considered similar to that of including performance status, either as stratification or prognostic covariates.

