3.2.4 Men and women, ages ≥ 18 years of age

3.2.5 ECOG performance status ≤ 2

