4.6 Stratification Factors and Treatment Assignments

4.6.1 Stratification Factors

1) Platinum Status: Ineligible vs. Refractory

- Platinum ineligible is defined as meeting any one of the following criteria: Impaired renal function [creatinine clearance (CrCl) of <30 mL/min], >2 peripheral neuropathy, or NYHA Heart Failure of >3.
- Platinum-refractory is defined as prior platinum-based perioperative chemotherapy within 12 months of relapse or prior platinum-based chemotherapy for metastatic disease.

2) Visceral Metastasis: Yes vs. No

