4.6.2 Treatment Assignments

Patients will be randomized 1:1 to the two treatment arms. The factors defined in [Section 4.8.1](#) will be used as stratification factors.

After the patient has been registered into the study, the values of the stratification factors will be recorded, and the patient will be randomized to one of the following treatment groups using the Pocock and Simon dynamic allocation procedure which balances the marginal distributions of the stratification factors between the treatment groups.

- 1) Immunotherapy
- 2) Immunotherapy + Single Site Radiotherapy

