 - 1 The PRO-CTCAE assessment is required for all patients. If the PRO-CTCAE assessment completed prior to registration is obtained \leq 14 days prior to treatment, then the PRO-CTCAE assessment on day 1 of cycle 1 may be skipped. The PRO-CTCAE patient-completed booklet for this protocol can be found on the 'CIRB Approved Documents' tab on the CTSU website.
 - 2 To be completed after registration and \leq 21 days prior to treatment.
 - 3 For women of childbearing potential. Must be done \leq 14 days prior to initiation of study treatment.
 - 4 See Section 6.2.

- 5 Baseline scans can include either: 1) a CT, spiral CT, or MRI and bone scan, or 2) an FDG-PET scan and diagnostic CT performed with both IV and oral contrast, and the CT acquired with 5 mm or less slice thickness. Supporting documentation is to be submitted, per Section 6.1.1.
- 6 ECG prior to registration should be performed if clinically indicated.
 - A All patients receiving immunotherapy will have a urinalysis or urine protein performed \leq 72 hours prior to every dose. If urine protein is \geq 2+, 24-hour urine collection or UPC ratio will be required.
 - B Required only if signs or symptoms suggestive of metastases develop.
 - C \leq 2 days prior to each treatment if accessible to physical examination.
 - D Every 3 months until evidence of progression or relapse. If the baseline scans were a CT or MRI and bone scan, follow-up bone scans are required only for patients with bone metastases as the only site of evaluable disease, and are optional for other patients. Response assessment should include assessment of all sites of disease and use the same imaging method as was used at baseline. Bone imaging (after baseline) is required only if indicative of metastases at baseline or if signs or symptoms suggestive of metastases develop.

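### The PFS and OS Cox models name no prognostic covariates, although ECOG status and the registration fatigue and QOL scores are collected; pre-specifying adjustment would be a cheap improvement

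*Combined protocol and SAP*

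**What the plan says.** On the survival analysis, Section 13.7 says: "For the secondary time-to-event endpoints, stratified Cox models will be used to compare the outcomes between the two treatment groups". No covariates are named and the strata are not listed. The natural reading is the two randomization factors of Section 4.6.1, "Platinum Status: Ineligible vs. Refractory" and "Visceral Metastasis: Yes vs. No".

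On the registration items, Section 1.2 says: "Baseline single-item assessments of fatigue and overall QOL are strong prognostic indicators for survival in cancer patients, independent of performance status". It adds: "Routine inclusion of these measures should be considered similar to that of including performance status, either as stratification or prognostic covariates".

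On performance status, eligibility is "ECOG performance status ≤ 2" (Section 3.2.5), and the Section 5.0 calendar has it recorded before registration.

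On timing, the calendar footnote for the fatigue/uniscale form reads "To be completed after registration and", followed by a limit of 21 days before treatment. Appendix I has the form given at patient registration and entered in the database at that time. Section 4.6.2 places randomization after registration too: "After the patient has been registered into the study, the values of the stratification factors will be recorded, and the patient will be randomized". Section 13.1 describes the trial as open-label.

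Covariates appear in two other analyses. Section 13.6 has an additional logistic model for response, using baseline variables found to be imbalanced. Section 14.1.4 allows prognostic factors in the QOL mixed models as an option. Neither concerns PFS or OS.

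**The concern.** The protocol gives a reason for collecting the fatigue and QOL items from every patient, and Section 13 contains no analysis that uses them for that reason. ECOG status, the familiar example to which Section 1.2 compares them, is also unused in the survival comparison, although patients with ECOG 0 to 2 are enrolled.

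In a Cox model, leaving out a baseline variable that predicts survival pulls the treatment hazard ratio toward 1 and lowers power. Comparing PFS and OS is a stated secondary objective (Section 2.2.2), and with 136 evaluable patients the number of deaths limits precision. Any adjustment also has to be written down before outcomes are seen, because covariates chosen afterwards carry little weight.

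**Working it through.** **1. The plan's own figure.** The only sample-size figure is for response (Section 13.4): 20% against 40%, one-sided alpha 0.10, power 90%. Per arm,

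n = [1.2816·√(2·0.3·0.7) + 1.2816·√(0.2·0.8 + 0.4·0.6)]² / 0.2² = (0.8306 + 0.8105)² / 0.04 = 67.3, so 68 per arm and 136 in total. Then 136/0.95 = 143.2, so 144.

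This reproduces the plan, but says nothing about survival. No hazard ratio, event count, alpha or power is given for PFS or OS.

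**2. Inputs for OS.** From the documents:
- 136 patients, 1:1 (Sections 13.4 and 4.6.2).
- Three years of follow-up (Section 13.5).
- Median OS of 10.3 months on pembrolizumab in the phase III trial cited in Section 1.1, used here for the control arm.
- One-sided 0.10, borrowed from the response endpoint.

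Assumed, because the documents are silent:
- Conditional hazard ratios of 0.65 and 0.75.
- ECOG 0/1/2 in 40/45/15%.
- Platinum-ineligible 30% and visceral disease 70%, with log-hazard effects 0.2 and 0.4.
- Fatigue and QOL standardized, correlated 0.6, and independent of ECOG.
- Exponential survival, and simple 1:1 allocation without the dynamic procedure.

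**3. Model.** The hazard is (ln 2/10.3)·exp[ln HR·arm + βE·(ECOG − 0.75) + βF·fatigue + βQ·QOL + strata effects]. Each simulated trial was analyzed by a Cox model stratified on the two factors, with and without the three covariates (Wald test, 8,000 trials per setting).

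Assumed hazard ratios per ECOG level, per SD of fatigue and per SD of QOL:
- Weak: 1.22, 1.11, 1.11.
- Moderate: 1.49, 1.22, 1.16.
- Strong: 1.82, 1.42, 1.28.

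| True HR | Covariates | Deaths | Power, strata only | Power, adjusted | Gain (points) | Mean HR, strata only |
|---|---|---|---|---|---|---|
| 0.65 | null | 115 | 83.3% | 82.9% | −0.4 | 0.647 |
| 0.65 | weak | 114 | 82.5% | 83.4% | 0.9 | 0.655 |
| 0.65 | moderate | 113 | 77.6% | 82.3% | 4.7 | 0.673 |
| 0.65 | strong | 109 | 68.2% | 80.8% | 12.6 | 0.706 |
| 0.75 | null | 118 | 59.5% | 59.2% | −0.3 | 0.748 |
| 0.75 | weak | 117 | 57.2% | 59.2% | 2.0 | 0.756 |
| 0.75 | moderate | 115 | 53.7% | 58.8% | 5.1 | 0.768 |
| 0.75 | strong | 112 | 47.1% | 57.1% | 10.0 | 0.790 |

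The adjusted mean HR stays at 0.640 to 0.644 and 0.743 to 0.744.

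**4. Cross-check.** Schoenfeld's approximation, power = Φ(½·√d·|ln HR| − 1.2816), with d = 115 and HR 0.65 gives Φ(5.362·0.4308 − 1.2816) = Φ(1.028) = 85%. The simulated null case gives 83.3%; the approximation ignores the cost of stratifying.

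**5. A simpler simulation.** This used 144 patients, HR 0.70, one normal prognostic score, no strata and 1,500 trials per setting. Power without and with the score was:
- SD 0.3: 71.3% and 74.9%, gain 3.6.
- SD 0.5: 65.9% and 74.5%, gain 8.6.
- SD 0.7: 59.1% and 73.4%, gain 14.3.

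Its comparator is not the planned stratified model, so it supports the direction and supplies only the upper end of the range.

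To compare scales, the prognostic variance in step 3 is βE²·0.4875 + βF² + βQ² + 1.2·βF·βQ, where 0.4875 is the assumed ECOG variance:
- Weak (β = 0.2, 0.1, 0.1): 0.0195 + 0.032 = 0.0515, SD 0.23.
- Moderate (0.4, 0.2, 0.15): 0.078 + 0.0985 = 0.1765, SD 0.42.
- Strong (0.6, 0.35, 0.25): 0.1755 + 0.290 = 0.4655, SD 0.68.

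On this scale the two simulations agree broadly. ECOG alone carries 38%, 44% and 38% of the assumed variance, so adjusting for ECOG only should gain less than the table shows. That case was not simulated.

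**6. Type I error.** At HR 1.0, rejection was 9.8 to 10.6% strata-only and 10.2 to 11.4% adjusted. The Monte Carlo standard error is √(0.1·0.9/8000) = 0.3 points. The excess of 0.3 to 0.8 points within scenarios means a small part of the gain may be inflation.

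**The case against.** The strongest reply is that a stratified Cox model is a valid and common choice, consistent with the stratified Mantel-Haenszel test used for response, and that nothing in the plan bars a supportive adjusted model. That stands: this is an improvement to the plan, and the planned analysis is not in error. The strata-only hazard ratio of 0.71 where the conditional value is 0.65 reflects non-collapsibility; the two are different estimands.

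Several stronger readings are tempting and are not supported:
- A reader might infer that Section 1.2 says ECOG is collected to be a covariate. It names performance status only as the comparator for the fatigue and QOL items, and it is a general recommendation that does not commit this trial to a model.
- A reader might infer that PFS and OS drive the phase 3 decision. The envisioned outcomes in Section 1.1 do not name them, and Section 13.7 gives the key secondary role to response by iRECIST.
- A reader might infer that adjustment costs nothing. The calendar places the fatigue/QOL form after registration, and randomization also follows registration in an open-label trial, so some scores could be given after the arm is known. Appendix I points the other way. This difference has to be settled before the scores can serve as baseline covariates. No such doubt arises for ECOG.

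**Conclusion.** The point holds as a cheap improvement. The survival models name no covariates, ECOG is available before registration, and a recommendation in Section 1.2 is not carried into Section 13. For OS, adjusting for all three variables changes power by about 0 points if they are null and adds 1 to 2 if weak, about 5 if moderate and 10 to 14 if strong. The sponsor's own description of the fatigue and QOL items as strong argues against the null end, but the documents give no prognostic hazard ratio that would fix the value. The figures also rest on the assumed treatment effects and patient mix and on a borrowed alpha. They should not be carried over to PFS, for which the documents give no median. If only ECOG can be used, expect less than these figures.

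**What to change.** In Section 13.7, pre-specify wording such as: PFS and OS will each be compared with a Cox model stratified by platinum status and visceral metastasis and adjusted for baseline ECOG performance status, with the coding and the handling of missing values fixed in advance; the model with strata only will be reported alongside. State which of the two is the main analysis.

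Reconcile the calendar footnote with Appendix I. If the form is then completed before randomization for all patients, add the fatigue and overall-QOL scores to the adjusted model under the same rules. Otherwise adjust for ECOG alone, as one decision for the whole trial and not patient by patient.

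The ECOG part costs a few lines of text and no new data. Using the fatigue and QOL scores also needs the timing clarified and followed at sites. The remaining downside is small: the adjusted hazard ratio is conditional on the covariates, so the report must say which estimand each model gives.

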2.2 Secondary objectives

- 2.2.1 To compare the response rates using iRECIST as assessed by central review
- 2.2.2 To compare progression-free survival (PFS) and overall survival (OS) for patients treated with immunotherapy and immunotherapy plus radiotherapy
- 2.2.3 To compare the rates of treatment discontinuation at 1 year
- 2.2.4 To assess adverse events experienced by patients treated with immunotherapy and immunotherapy plus radiotherapy via the CTCAE and PRO-CTCAE.

2.2.5 To determine whether treatment effects are similar for key subgroups including those defined by the stratification variables.

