13.2 Study Endpoints

13.2.1 Primary Endpoint

The primary endpoint is tumor response within 6 months of randomization. Tumor response is defined as a complete response (CR) or partial response (PR) as assessed by the treating physician using RECIST v1.1 criteria.

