13.3 Subgroup Analysis

Subgroup analysis may be conducted in the following groups for efficacy endpoints including tumor response, PFS, and OS.

- 1) Platinum status: platinum ineligible versus platinum refractory
- 2) Visceral metastasis: present versus absent

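### The subgroup plan reports no between-level contrast for PFS or OS and gives no subgroup method for tumor response, so its output does not directly address objective 2.2.5

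*Combined protocol and SAP*

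**What the plan says.** Section 2.2 lists as a secondary objective: "To determine whether treatment effects are similar for key subgroups including those defined by the stratification variables".

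Section 13.3 is worded as an option: "Subgroup analysis may be conducted in the following groups for efficacy endpoints including tumor response, PFS, and OS". It names two factors, each with two levels: "Platinum status: platinum ineligible versus platinum refractory" and "Visceral metastasis: present versus absent". These are the randomization stratification factors of section 4.6.1.

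The only subgroup method is in section 13.7, in the paragraph on time-to-event endpoints. It is a stratified Cox regression with arm as the covariate, fitted level by level: "a separate model will be generated for each level for the subgroup of interest". The output is then fixed: "The results will be summarized with a forest plot displaying the estimate of the hazard ratio and corresponding 95% confidence interval".

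Section 13.2.1 makes the primary endpoint binary: "The primary endpoint is tumor response within 6 months of randomization", where response means CR or PR. Section 13.6 analyses it overall with a Mantel-Haenszel test and a supporting logistic regression on arm and imbalanced baseline variables. Neither is specified for subgroups. The only interaction term in the documents is arm by time, in the quality-of-life mixed model of section 14.1.4.

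**The concern.** Whether two effects are similar is a question about the difference between them. Two separate hazard ratios, each with its own interval around its own estimate, describe the levels but do not report that difference or its uncertainty. A common misreading of such a forest plot is to take one interval that excludes 1 and one that includes 1 as evidence that the effects differ. That pattern arises often by chance when the true effects are equal.

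For tumor response the gap is wider. It is the primary endpoint and is named in 13.3, yet the plan does not say how its subgroup effects will be estimated or compared, and a hazard ratio does not apply to a yes/no outcome.

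Section 1.1 says the trial should guide later phase II trials and possibly a phase III trial. A spurious subgroup signal could influence who is enrolled in them.

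**Working it through.** **Inputs from section 13.4:** one-sided alpha 0.10, power 90%, response 20% versus 40%, 68 evaluable per arm. **Assumed, because the documents do not give them:** the split of patients between levels, the PFS/OS hazard ratio and event count, and the size of any true heterogeneity.

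**1. The plan's own sample size.** With pooled variance and mean rate 0.30:

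n = 1.2816² × (√(2 × 0.30 × 0.70) + √(0.20 × 0.80 + 0.40 × 0.60))² / 0.20² = 1.2816² × (0.648 + 0.632)² / 0.04 ≈ 67.3, so 68 per arm and 136 in total. This matches the plan. Also 136 / 0.95 = 143.2, so 144, the target accrual. Simulated power with the futility rule is 89.9%.

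**2. Discordance for response with the same true effect in both levels.** Overall drift = 1.28 + 1.28 = 2.56. Drift in a level holding share s of the patients = 2.56 × √s. The chance that its 95% interval excludes no effect in the direction of benefit is p = Φ(2.56√s − 1.96). The levels contain different patients, so the chance that exactly one interval excludes no effect is p₁(1 − p₂) + p₂(1 − p₁).

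| Assumed split | p₁ | p₂ | Exactly one excludes no effect |
|---|---|---|---|
| 50/50 | 0.44 | 0.44 | 49% |
| 70/30 | 0.57 | 0.29 | 53% |
| 80/20 | 0.63 | 0.21 | 58% |

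Using the two-proportion power formula directly (20% versus 40%, two-sided 0.05) gives 49.1%, 53.0% and 57.6%.

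**3. The same check for PFS and OS.** The documents give no power, hazard ratio or event count here. Assume a common hazard ratio of 0.7 (|log HR| = 0.357) and variance 4/events in each level.

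- 80 events split 50/50: SE = √(4/40) = 0.316; p = Φ(0.357/0.316 − 1.96) = 0.203; discordance = 2 × 0.203 × 0.797 = 32%.
- 120 events split 30/70: p = 0.187 and 0.372; discordance = 0.187 × 0.628 + 0.372 × 0.813 = 42%.

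The other combinations tried (80, 100 and 120 events, splits 50/50 and 30/70) lie between these.

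**4. What an interaction test could detect** (two-sided 0.10, control rate 20% in both levels, 68 per arm). For gains of +30 versus +10 points with a 50/50 split, the SE of the difference in log odds ratios is

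√(1/(34 × 0.16) + 1/(34 × 0.25) + 1/(34 × 0.16) + 1/(34 × 0.21)) = 0.791.

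The true difference is 0.847, so power = Φ(0.847/0.791 − 1.645) = 28%. Other cases:

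| Assumed heterogeneity | Split | Log odds ratio | Risk difference |
|---|---|---|---|
| +30 vs +10 points | 50/50 | 28% | 37% |
| +30 vs +10 points | 30/70 | 26% | 33% |
| +40 vs 0 points | 50/50 | 71% | 87% |
| +40 vs 0 points | 30/70 | 65% | 79% |

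For PFS or OS with a ratio of hazard ratios of 0.5 and 80 to 120 events, power is 41% to 60%.

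**The case against.** A reader might infer that the plan cannot answer objective 2.2.5 at all. For PFS and OS the documents do not support that. The levels are independent, so the ratio of hazard ratios and its interval can be derived from the planned estimates. What is missing is a reported contrast.

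A reader might also infer that the primary endpoint has no model, or that the plan fits a Cox model to a binary outcome. Neither holds. Section 13.6 names overall analyses for response, and the Cox sentence sits in the time-to-event paragraph. The fair reading is that the plan is silent on how response will be analysed by subgroup.

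Three further objections have weight:

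- The 49% to 58% rests on design power stated only for response, while the separate-model procedure is stated for PFS and OS. It is an illustration; for PFS and OS the relevant range is 32% to 42%, on assumed inputs.
- Section 13.7 sets no within-level test or decision rule. The discordance figures describe a common misreading, not a rule in the plan.
- An interaction test here has low power, so it cannot establish similarity either. Its value is the direct estimate of the difference with its interval.

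The optional wording in 13.3 and the secondary role of the analysis limit the importance of the point. They do not remove it, because 2.2.5 is a listed objective.

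**Conclusion.** The point holds in this form: 13.7 gives separate PFS and OS effects by level without a between-level contrast, and response, listed in 13.3, has no subgroup method. The output does not directly address 2.2.5. This follows from the text and needs no assumption.

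The size of the risk of misreading does need assumptions. It is about 49% to 58% for response (design power, equal true effects, splits from 50/50 to 80/20) and about 32% to 42% for PFS and OS (hazard ratio 0.7, 80 to 120 events, splits 50/50 or 30/70). The primary test, sample size and futility rule are unaffected.

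**What to change.** Amend 13.7 so that, for each of the two factors:

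- **Tumor response** is analysed by logistic regression with arm, the factor, the other stratification factor and an arm-by-factor term.
- **PFS and OS** are analysed by a Cox model stratified by both randomization factors, with arm and an arm-by-factor term. Taking the plan's stratification to be by those factors, the partial likelihood separates by stratum, so this model reproduces the planned per-level hazard ratios and adds the contrast. Stratifying by the other factor alone would add an unneeded assumption of proportional hazards between subgroup levels.
- **Reporting:** give the interaction estimate (ratio of odds ratios or of hazard ratios) with its interval beside the forest plot. Label it exploratory, and state that because power is low a non-significant interaction does not establish similarity.

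Also reconcile the optional wording of 13.3 with objective 2.2.5.

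The cost is a few sentences and a little extra analysis, with no new data and no change in sample size. The interaction estimate will be imprecise. Making the change before the data are analysed keeps it prespecified.
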